### **3.2 Safety Analysis Set**

The safety analysis set will contain all eyes for which LenSx is activated and laser cut is started for the test eyes and corneal incision is begun for the control eyes; all eyes in the safety analysis set will be assigned to the procedure group actually received. The safety analysis set will be the primary analysis set for all summaries and analyses of safety data.

## **4 Subject Characteristics and Study Conduct Summaries**

### **4.1 Subject Disposition**

A subject disposition table based on the FAS will be presented that displays the number and percentage of subjects who completed or discontinued the study prematurely including the reason for discontinuation. In addition the total number and percentage of subjects passing and failing screening will be presented for all screened patients. A patient accountability table for subjects with at least one eye in the FAS will be provided based on Table C.1 in ANSI Z80.12-2007.

The number of eyes within each of the analysis sets ([Section 3.1](#) and [Section 3.2](#)) used in the study will be given. The reasons for exclusion from each set will be listed.

### **4.2 Protocol Deviations**

The number of protocol deviations (PDs) will be tabulated by deviation code. In addition, a listing of PDs will be produced including the accompanying deviation code.

### 4.3 Demographics and other Baseline Characteristics

Characteristics by subject will be summarized overall, and characteristics by eye will be summarized by procedure group and overall.

Demographics and background characteristics for each subject:

- Age (in years, and year categories < 65 and ≥ 65)
- Gender (male / female / unknown / undifferentiated)
- Ethnicity (Hispanic or Latino / not Hispanic or Latino / not reported / unknown)
- Race (White / Black or African American / American Indian or Alaska Native / Asian / Native Hawaiian or Other Pacific Islander / other)

Ocular characteristics for each eye:

- Axial length (mm)
- Keratometry

Note: variables that have both baseline and post-baseline values will be summarized elsewhere in the SAP: Intraocular pressure (IOP), ██████████ ██████████ manifest refraction, slit lamp examination.

### 4.4 Medical History

Relevant medical history (ocular and non-ocular) and current medical conditions by eye will be listed by surgery group for data in the FAS.

### 4.5 Prior and Concomitant Medications

Prior (or previous) medications are defined as those medications which were taken and stopped prior to surgery.

Concomitant medications are medications taken after surgery but prior to the last day of study visit. They also include medications initiated pre-surgery which continued into the post-surgery period. Note that this will not include routine preoperative, intraoperative and postoperative medications administered for the cataract surgery.

Prior or concomitant medication will be identified based on recorded or imputed start and end dates of medication taken. Prior and concomitant medications will be coded according to the

World Health Organization (WHO) Drug Reference List dictionary (201603 or a more recent version) which employs the Anatomical Therapeutic Chemical (ATC) classification system.

Prior and concomitant medications by eye will be listed by procedure group for data in the safety analysis set.

## **5 Effectiveness Analysis Strategy**

[figure not shown]
### **5.1 Effectiveness Endpoints**

#### **Primary endpoint**

- Percentage of eyes in which the MRSE at 1 month is  $\leq 0.5D$  relative to predicted MRSE

#### **Secondary endpoints**

- Mean CDE expended in the eye during surgery
- Mean estimated aspiration fluid used during surgery
- Mean aspiration time spent during surgery.

## 5.2 Effectiveness Hypotheses

### 5.2.1 Primary Effectiveness Hypotheses

The primary effectiveness objective is to demonstrate superiority of the CRS compared to standard manual techniques with respect to refractive predictability at Month 1. The following hypotheses will be tested:

$$H_0: p_c \leq p_s$$

$$H_1: p_c > p_s$$

where  $p_c$  and  $p_s$  are the percentage of eyes with manifest refraction spherical equivalent within 0.5D of predicted postoperative spherical equivalent at Month 1 in the CRS and standard manual technique arms respectively.

[figure not shown]
### 5.2.2 Secondary Effectiveness Hypotheses

The null and alternative hypotheses are the same for all secondary analysis and can be presented as:

$$H_0: \mu_c \geq \mu_s$$

$$H_1: \mu_c < \mu_s$$

where  $\mu_c$  denotes the mean value in the CRS group and  $\mu_s$  denotes the mean value in the standard manual technique group for each of the respective secondary endpoints (mean CDE expended in the eye during surgery, mean estimated aspiration fluid used during surgery, and mean aspiration time spent during surgery).

## 5.3 Statistical Methods for Effectiveness Analyses

All analysis in this section will be based on the FAS.

### 5.3.1 Primary Effectiveness endpoint

[figure not shown]
The primary effectiveness analysis will be analyzed using a one-sided McNemar's test at the 5% significance level. P-value for the difference in the population proportions will be estimated and presented.

[figure not shown]
The number and percentage of eyes with manifest refraction spherical equivalent  $\leq 0.5D$  of predicted post-operative spherical equivalent will be presented by surgery procedure and visit.

### 5.3.2 Secondary Effectiveness Endpoints

Each of the null hypotheses will be tested using a one-sided paired t-test. Multiplicity adjustment will be discussed in Section 5.4.

Descriptive statistics for continuous variables will be provided by procedure group for each of the secondary effectiveness endpoints (mean CDE expended in the eye during surgery, mean estimated aspiration fluid used during surgery, mean aspiration time spent during surgery).

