7.2 Clinical Study Design

This is a prospective, multi-center, observer-masked, randomized, active control (standard manual technique), contralateral design study to evaluate refractive predictability between CRS and standard manual technique. All products under investigation are commercially available in the countries where the study is being conducted.

The eye with the worse preoperative best-corrected distance visual acuity (BCDVA) will undergo cataract surgery with IOL implantation first. If the preoperative BCDVA is equal in both eyes, then the right eye will undergo the surgery and IOL implantation first. The first eye will be randomized to receive the test or control treatment; the fellow eye will receive the opposite assignment. Subjects are required to attend 8 study visits, during which assessments will be scheduled separately for the first study eye, the second study eye and both study eyes.

[figure not shown]
Subjects will attend the Screening visit from Day -30 to Day -1 (Surgery Eye 1, Visit 00), followed by Visit 1 (Day 1 post surgery for Eye 1), Visit 00A (Surgery Eye 2 [7-14 days after that for Eye 1]), Visit 1A for both eyes (Day 1 for Eye 2; Day 8-15 for Eye 1), Visit 2A (Day 7-10 post Eye 2 surgery), Visit 3A (Month 1 [Day 20-40 post Eye 2 surgery]), Visit 4A (Month 3 [Day 70-110 post Eye 2 surgery]). Total expected clinical study duration will be approximately 5 months after being screened for study eligibility.

This study will employ an adaptive design with a potential sample size adjustment based on interim analysis (Section 15.8). It is planned that the study will enroll approximately 350 subjects to initially randomize and treat 300 subjects (that could potentially increase to approximately 580 subjects enrolled and 500 subjects randomized). An interim analysis will be performed once 200 subjects have been randomized, treated and completed 1-month follow-up visits. An additional 200 subjects may be randomized and treated beyond the initially planned 300 subjects. Thus the study will randomize and treat between 300 and 500 subjects.

An overview of the study design is presented in **Figure 7-1**.

Figure 7-1

Study Design

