9.3 Procedures Conducted at each Study Visit

Procedures required by the protocol to be conducted at each study visit are listed in the [Table 6-1](#) and detailed in Section [12](#) and in the manual of procedures (MOP) that accompanies this protocol. A brief summary of the main procedures performed by visit is provided here.

- At the Screening visit (Visit 0) the subject will sign informed consent. Standard procedures will be performed to determine subject eligibility.
- Following confirmation of eligibility, the surgery visit will be scheduled for the first study eye. The subject will be randomized (via the Medidata RAVE) prior to the first surgery visit to a technique sequence. The technique sequence will be randomly assigned as either: CRS then standard manual technique or standard manual technique then CRS.
- At the surgery visit (Visit 00), if subjects are randomized to CRS, the test devices to be used on the first eye during surgery will be: Verion (digital marker L, digital marker M), LenSx device, VerifyEye+ measurement with or without VerifyEye Lynk. The estimated aspiration fluid, phacoemulsification aspiration time, and CDE will be recorded for both arms of the study. The subject will then undergo surgery in the other eye using a standard manual technique and perform manual LRI as needed as indicated on the MOP (Visit 00A).
- At the post-surgery follow-up visits, ie, Visit 1 (for the first study eye), Visit 1A (for both study eyes), Visit 2A (for the second study eye), Visit 3A and Visit 4A (for both eyes), the following assessments will be performed: concomitant medications, [REDACTED] manifest refraction, slit-lamp examination, AEs and device deficiencies will be recorded in all post-surgery follow-up visits.
 - o IOP measurements will be performed at Visit 1A and Visit 4A.
 - o Dilated fundus examination will be performed at Visit 4A.
 - o Keratometric measurements will be performed at Visit 3A and Visit 4A.

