15.2 Analysis Data Sets

The full analysis set (FAS) will contain all eyes that are randomized and for which an IOL is successfully implanted; all eyes in the FAS will be assigned to the treatment actually received for analysis purposes. The FAS will be the primary analysis set for all effectiveness summaries and analyses, as well as all baseline and study summaries.

The safety analysis set will contain all eyes for which LenSx is activated and laser cut is started for the test eyes and corneal incision is begun for the control eyes; all eyes in the safety analysis set will be assigned to the treatment actually received. The safety analysis set will be the primary analysis set for all summaries and analyses of safety data.

Assignment of study eyes to the appropriate analysis set(s) will be determined prior to database lock.

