15.4.2.2 Analysis Methods

Each of the null hypotheses will be tested using a paired *t*-test; the family-wise type-I-error of 5% will be controlled using the Hochberg testing procedure outlined in Section 15.6.

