### **1.3 Randomization**

A member of the Randomization Programming group at Alcon who is not part of the study team will generate the randomized allocation schedule for surgery procedure group. Randomization will be implemented in an Interactive Response Technology system.

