## **3 Analysis Sets**

### **3.1 Effectiveness Analysis Sets**

The full analysis set (FAS) will contain all eyes that are randomized and for which an IOL is successfully implanted; all eyes in the FAS will be assigned to the surgery procedure actually received for analysis purposes. The FAS will be the primary analysis set for all effectiveness summaries and analyses, as well as all baseline and study summaries (i.e. subject disposition, background and demographic characteristics, medical history).

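### Optional improvement: the paired t-tests on the three secondary endpoints could use the randomised eye order, at a cost of about one degree of freedom

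*SAP*

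**What the plan says.** The three secondary endpoints are confirmatory. They are tested only if the primary null hypothesis is rejected, and then by Hochberg's procedure (Protocol 15.6, SAP 5.4).

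- **Test.** SAP 5.3.2: "Each of the null hypotheses will be tested using a one-sided paired t-test". Protocol 15.4.2.2 also names a paired t-test and adds that "the family-wise type-I-error of 5% will be controlled using the Hochberg testing procedure outlined in Section 15.6". Neither section mentions eye order, period or sequence.
- **What is randomised.** Protocol 9.3: "The technique sequence will be randomly assigned as either: CRS then standard manual technique or standard manual technique then CRS".
- **Which eye goes first.** Protocol 7.2: "The eye with the worse preoperative best-corrected distance visual acuity (BCDVA) will undergo cataract surgery with IOL implantation first". For ties: "If the preoperative BCDVA is equal in both eyes, then the right eye will undergo the surgery and IOL implantation first". The second eye follows 7 to 14 days later.
- **Allocation.** SAP 1.3 says only that a member of a separate programming group "will generate the randomized allocation schedule for surgery procedure group". It gives neither the ratio nor any blocking.
- **Grouping.** Effectiveness is analysed as treated. SAP 3.1: "all eyes in the FAS will be assigned to the surgery procedure actually received for analysis purposes". Protocol 15.2 has the same rule.

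**The concern.** Surgical order is not arbitrary here, because it carries preoperative acuity. It is therefore plausible that first and second eyes differ on average in energy, fluid or aspiration time. That is an inference: neither document says so.

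If they do differ, each subject's paired difference contains the order difference, with one sign when CRS comes first and the opposite sign when it comes second. The planned t-test treats this known, randomised source of variation as noise. If the two sequences end up uneven, part of it also moves the estimate. At stake are some power for three confirmatory tests and, for the split actually obtained, how closely the nominal error rate is met. Because sequence is randomised and recorded, the component can be removed without new data.

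**Working it through.** **1. The plan's own figure.** The documents give sample size and power only for the primary endpoint. With the Miettinen approximation (discordance ψ, difference Δ = 0.08, one-sided 5%, 90% power):

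n = [z₀.₉₅ψ + z₀.₉₀√(ψ² − Δ²(3+ψ)/4)]² / (ψΔ²)

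ψ = 0.21 gives 266.4, so 267. ψ = 0.33 gives 432.0, so 433. Both match SAP 7. I use 267 below only as the number of pairs.

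**2. Model.** Sign the paired difference so that benefit of CRS is positive. Its mean is τ + d in one order and τ − d in the other, with SD s within each order. The documents give none of τ, d or s, so d/s is an assumed range. I take the τ at which the order-adjusted test has 80% power with 267 pairs: τ/s = 0.1526 at one-sided 5%, and 0.1825 at the strictest Hochberg step (0.05/3 = 1.67%).

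**3. Balanced orders.** Both tests give the same estimate, with true standard error s/√267 = 0.0612s. The planned test takes its variance as s² + d², and the adjusted test as s². At d/s = 0.5 the planned standard error is √(1.25/267) = 0.0684, so it rejects above 1.65 × 0.0684 = 0.1129. Its power is Φ((0.1526 − 0.1129)/0.0612) = Φ(0.65), about 74%. Simulation gives:

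| d/s | Planned power, balanced, 5% | Planned power, simple 1:1 randomisation, 5% | Planned power, balanced, 1.67% | Planned power, simple 1:1, 1.67% | Planned type I error, balanced, 5% | Pairs lost, balanced, 5% |
|---|---|---|---|---|---|---|
| 0 | 80.0 | 80.0 | 80.0 | 80.0 | 5.0 | 0 |
| 0.1 | 79.8 | 79.6 | 79.7 | 79.6 | 4.9 | 2 |
| 0.2 | 79.1 | 78.6 | 78.8 | 78.4 | 4.7 | 7 |
| 0.3 | 77.9 | 77.0 | 77.3 | 76.3 | 4.3 | 15 |
| 0.5 | 74.1 | 71.9 | 72.3 | 70.1 | 3.3 | 40 |

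(Power and error in %.) At the 5% level the adjusted test has 80.0% power with balanced orders and about 79.9% under simple randomisation. Averaged over simple randomisation, the planned test's type I error is 5.0%.

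**4. An uneven split.** Take 147:120 and d/s = 0.3, with no treatment effect. The estimate shifts by 0.3 × 27/267 = 0.030s. The planned standard error is √[(1 + 0.09(1 − (27/267)²))/267] = 0.0639, so the test rejects above 1.65 × 0.0639 = 0.105. The conditional error is then about 1 − Φ((0.105 − 0.030)/0.0612) if the shift favours CRS, or 1 − Φ((0.105 + 0.030)/0.0612) if it goes the other way. Simulation gives 11.1% and 1.4%; the adjusted test gives 5.0%. Under simple randomisation, a split at least this uneven has probability of about 11%.

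**5. Which variance.** Holding 5% with a pooled within-order variance needs equal variances in the two orders or a balanced split. At 147:120 with an assumed within-order SD ratio of 1.5, the pooled version gives 5.7% or 4.4%, depending on which group has the larger SD. The separate-variance version, with standard error ½√(s₁²/n₁ + s₂²/n₂), gives 5.0%. With equal variances it reproduces the adjusted figures above to the rounding shown.

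**6. A larger true effect.** With τ/s = 0.25 (assumed), 300 balanced pairs and the 1.67% level, planned against adjusted power is 98.4% against 98.5% at d/s = 0.2, and 97.3% against 98.6% at d/s = 0.5.

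**7. If d = 0.** The adjustment costs about 0.1 point of power on average under simple randomisation, and about 0.4 point at 147:120.

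**The case against.** The strongest case against is that nothing here is broken. Randomising the technique given to the first eye is the design's own protection against eye order, and whether to add an order term to a valid test is a matter of preference. The benefit rests on a d that the documents do not give. The power figures are anchored at 80%, near where a variance gain shows most, while Protocol 9.4.2 expects the laser to reduce phaco power and time, so the true effect may be large. The 11.1% is one assumed d combined with one split, and blocking, on which SAP 1.3 is silent, might rule that split out. Finally, SAP 1.4 lets sponsor and site staff know the surgery assignment, so it is hard to show that a late change to a confirmatory test was made blind to results.

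Most of this stands, and it limits the size and rank of the point. It does not remove it: the change needs no new data, costs almost nothing if d = 0, and protects against an imbalance that the text does not exclude. The credibility cost is real and argues for making the change early and dating it.

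Three stronger readings are tempting and are not supported. A reader might infer that operating on the worse eye first confounds the comparison. It does not, because technique is randomised within that order. A reader might infer that the type I error of the secondary tests is 11%. On average it is 5.0%, and with balanced orders it is 5% or less. A reader might infer that the secondary endpoints are underpowered. The documents make no power claim for them, so none is undermined.

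**Conclusion.** A low-priority improvement. The planned paired t-tests are valid on average over the randomisation and no stated figure is wrong. The plan leaves unused a randomised factor that may carry a real difference between eyes.

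At one-sided 5%, the planned test gives up 80.0 − 79.1 = 0.9 to 80.0 − 78.6 = 1.4 points at d/s = 0.2, and 80.0 − 74.1 = 5.9 to 79.9 − 71.9 = 8.0 points at d/s = 0.5. At the strictest Hochberg step the d/s = 0.5 loss is about 8 to 10 points. The gain is nil if d = 0 and about 1 point or less in the larger-effect examples.

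These sizes rest on assumed values of d/s and τ/s, normal paired differences, 267 pairs (300 for the larger effect), and either balanced or simple 1:1 allocation. Only the average order effect is removed. The primary McNemar test is not in question.

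**What to change.** Amend SAP 5.3.2 before database lock and before any secondary outcome is viewed by procedure group. Suggested content:

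> For each FAS subject with one eye treated by each procedure, compute the CRS-minus-manual difference by procedure actually received. Group subjects by the order in which the procedures were actually received. The treatment effect is the equally weighted mean of the two group means, tested one-sided with standard error ½√(s₁²/n₁ + s₂²/n₂) and Welch–Satterthwaite degrees of freedom.

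Using the order actually received fits the as-treated FAS rule and keeps the right sign for a subject treated in the opposite order. A subject with both eyes treated the same way has no CRS-minus-manual difference under either method. Keep the hypotheses in SAP 5.2.2, the Hochberg steps in SAP 5.4 and the primary analysis.

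**Cost.** A few sentences and a few lines of code, about one degree of freedom (265 instead of 266 at 267 pairs), and the small power loss at d = 0 shown above. Until Protocol 15.4.2.2 is aligned at the next amendment, which needs ethics approval under Protocol section 5, SAP and protocol will name different tests. Record this, with its date, as a planned deviation, for which SAP section 1 already provides.

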## 5.4 Multiplicity Strategy

In order to control the overall type I error rate over the family of primary and secondary hypotheses, the secondary effectiveness hypotheses will only be tested if the primary effectiveness null hypothesis is rejected at the one-sided 5% significance level ( $\alpha=0.05$ ).

If the null hypothesis of the primary effectiveness endpoint is rejected, then the three secondary effectiveness endpoints will be tested using the Hochberg testing procedure. Let:

- $H_{0i}$  refers to the corresponding null hypotheses ( $i=1, 2, 3$ )

- $p_i$  refers to the p-values for  $H_{0i}$ , which will be calculated without any multiplicity adjustment. The p-values will be sorted in order of magnitude such that  $p_1 \leq p_2 \leq p_3$
- Hochberg's step-up method will proceed as follows:
  - Step 1: If  $p_3 < \alpha$  (where  $\alpha$  is 0.05, 1-sided), reject all  $H_{0i}$  ( $i=1,2,3$ ) and stop; otherwise go to Step 2.
  - Step 2: If  $p_2 < \alpha/2$  (where  $\alpha$  is 0.05, 1-sided), reject  $H_{01}$  and  $H_{02}$  and stop; otherwise go to Step 3.
  - Step 3: If  $p_1 < \alpha/3$  (where  $\alpha$  is 0.05, 1-sided), reject  $H_{01}$  and stop.

## 5.5 Handling of Missing Data

The analyses of the effectiveness endpoints will be based on observed data (i.e. no imputation will be performed). The influence of missing data is expected to be minimal.

## 5.6 Interim Analysis for Effectiveness

An interim analysis for the purposes of sample size re-estimation will be performed when the first 200 subjects who are randomized and treated complete their assessment for the primary effectiveness endpoint at Month 1 (Visit 3A). Alcon staff not involved with the conduct of the trial will re-estimate the sample size based on the data from the first 200 subjects. These staff will provide the re-estimated sample size and the predicted conditional power of the final test statistic based on that sample size.

If the conditional power of the study is  $< 50\%$  for the largest allowable sample size (500 subjects), no additional sample size beyond the originally planned 300 subjects will be added, and termination of the study may be considered. Because additional sample size will not be added if the conditional power of the study is  $< 50\%$  at the maximum allowable sample size, any effect of the sample size modification on the type I error should be minimal (Mehta, 2000).

## 6 Safety Analysis Strategy

### 6.1 Safety Endpoints

The safety endpoints are:

- Adverse events
- Slit lamp examination
- IOP

- Surgical problems
- Dilated fundus examination
- Device deficiencies

